Nutritional Intervention-Clinical Trial Protocol

Title: Postprandial Inflammatory and Metabolic Responses Induced by the Authentic Ladotyri Mytilinis PDO Cheese and Italian Parmesan PDO Cheese

NCT IDENTIFIER: NCT05788887

16 December 2022

1. Protocol Summary

This is the protocol of a randomized, blinded and controlled nutritional intervention – clinical study to investigate the postprandial effect of consuming Authentic Ladotyri Mytilinis, PDO cheese on the lipid, glycemic profile and the oxidative status of the blood of healthy volunteers.

The acute nutritional intervention – clinical study is a cross over design (acute study), with two axes. The purpose of this study was the investigation of the postprandial metabolic responses, after the intake of a traditional, Ladotyri Mytilinis cheese, compared to corresponding responses after an Italian Parmesan cheese consumption, in healthy participants.

The study volunteers will be healthy, aged 18-65 years, residing during the intervention in Lemnos. The study will take place in the specially designed space of the Human Nutrition Unit, University of the Aegean and in voluntary collaboration with the General Hospital of Limnos. The duration of the study will be 7 days.

Participants will be randomly divided into two groups. During the first day, the first group will consume Italian Parmesan, PDO cheese (control group) and the second group will consume Authentic Ladotyri Mytilinis, PDO cheese (intervention group), together with two slices of bread, while 1 glass of water will be available for each volunteer [1st test period]. After a 7-day washout period, the same volunteers will come to the specially designed area and the process will be repeated, with the difference that the control group of the 1st day will belong to the intervention group, and the intervention group will belong to the control [2nd test period].

In each test period, blood samples will be taken from all consecutive volunteers in a fasted state, as well as 30 minutes, 1.5 and 3 hours after consuming meals. This will be followed by analysis of the samples and statistical processing of the results of the analyzes to present data regarding the acute effect of meal consumption on the postprandial biomarkers of lipemia, glycemia and oxidative stress in healthy volunteers.

2. Theoretical background and study objectives

2.1. Argumentation, Research evidence, Rigor of study

The existing scientific evidence indicates a correlation of the levels of postprandial lipid, glycemic biomarkers and oxidative stress markers, with chronic diseases, such as cardiovascular diseases, diabetes, etc. (Koutelidakis and Dimou, 2016). Recent nutritional interventions by the team in healthy volunteers, but also participants at high metabolic risk, have shown a beneficial effect of consuming functional foods, such as a functional spreadable cheese, enriched with mountain tea and orange peel, but also a functional refined olive oil, fortified with antioxidants components from orange peel, on postprandial markers of lipemia, glycemia and oxidative stress (Papagianni et al, 2021).

The findings of previous clinical studies-dietary interventions suggest that the consumption of a meal containing cheese can cause a significant increase in the concentration of triglycerides, 2 hours after taking the meal (Drouin-Chartier et al., 2016).

Olive oil, the main characteristic of the Mediterranean Diet, thanks to the bioactive compounds it has in its composition, has been extensively studied in recent years, in vitro and in vivo, highlighting its antioxidant, anti-inflammatory and other actions (Jędrusek-Golińska et al., 2020). In vitro evidence shows that cheese enriched with polyphenols may contribute to maintaining the integrity of polyphenols and antioxidant activity in the gastrointestinal environment (Lamothe et al, 2016). The postprandial effect of consuming functional foods rich in polyphenols (e.g. olive oil, grapes) in combination with meals rich in fats and carbohydrates has been evaluated with promising results, since they seem to have a beneficial effect on metabolic biomarkers and pathways, postprandial (Magrone et al., 2013).

Based on the aforementioned scientific evidence regarding the possible postprandial effect of the bioactive components of olive oil (in which the cheese is extracted for the production of the oil cheese) on specific biomarkers, the present nutritional intervention will be composed.

2.2. Study Objectives / Research Questions

Purpose

The purpose of this study was the investigation of the postprandial responses on serum total, HDL-, LDL- cholesterol, triglycerides, uric acid, glucose and plasma Total Antioxidant Capacity (TAC), after the intake of a traditional, Authentic Ladotyri Mytilinis cheese, compared to corresponding responses after an Italian Parmesan cheese consumption, in healthy participants.

Research Questions

The research questions of this clinical study are the following:

- ✓ Which is the acute effect of ALM-PDO cheese consumption, in the framework of a high-fat and carbohydrates meal, on the postprandial biomarkers of lipemia, glycemia and oxidative stress?
- ✓ Does the postprandial inflammatory and metabolic responses to ALM-PDO cheese differs, compared to Italian Parmesan PDO cheese? LDL- cholesterol and triglycerides determined at 3h after the meal intake, was set as the primary endpoint of the present, pilot study.

3. Summary presentation / study design

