3.1. Overview

A nutritional intervention – clinical study of self-comparison design (cross over design: acute study) will take place in a sample of healthy volunteers, where the difference in the effectiveness of the nutritional intervention will be evaluated in the same volunteer. This means that the response of lipemia, glycemia and oxidative stress biomarkers to the intervention meal will be compared with their response to the control meal, in the same volunteer each time. The specific research will be carried out in the specially designed area of

the Human Nutrition unit of the University of the Aegean and in collaboration with the hospital of Lemnos, with which a collaboration protocol has been concluded with the University of the Aegean.

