4.1. Sample size calculation

In order to note a 40% difference in the postprandial response of triglycerides and/or LDL-cholesterol and in order to have an 80% chance of a statistically significant difference between the studied groups at a significance level of 5%, a necessary sample of 10 subjects was calculated.

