6.3. Statistical analysis

After the above analyzes have been carried out using a special biochemical analyzer, the use of the statistical package SPSS (Statistical package for social sciences: SPSS) will follow in order to record, process and analyze the results of the study. The Kolmogorov–Smirnov test was applied to check normality. The main participants' characteristics will be analyzed by descriptive statistics. Differences in baseline values between groups for each biomarker tested, will be analyzed using a paired sample two tailed t test. Repeated ANOVA measures with Geisser–Greenhouse correction will be conducted, for serum total, HDL-, LDL- cholesterol, triglycerides, glucose, uric acid and plasma Total Antioxidant Capacity (TAC). If time or group was significant, multiple comparison post hoc Bonferroni test will be performed for the comparison of concentrations. To check changes in the metabolic biomarkers from baseline to postprandial responses (within-group variation), the Wilcoxon sign-rank test will be carried out.

7. Maintenance of study records

The study files will remain securely registered for a maximum of 3 years from the date of their registration in special areas of the Human Nutrition Unit, University of the Aegean. Study records should be kept for a maximum of 2 years after the last marketing approval, or longer if required by local regulations.

8. Ethics, Consent and Privacy Statement

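### The aim is the postprandial response, but no adjustment for the same visit's fasting value is specified in the between-cheese comparison of the 3 h primary lipids

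*Combined protocol and SAP*

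**What the plan says.** The question is put as one of response in three places. Section 2.2 opens: "The purpose of this study was the investigation of the postprandial responses on serum total, HDL-, LDL- cholesterol, triglycerides, uric acid, glucose". Section 3.1 describes the contrast: "the response of lipemia, glycemia and oxidative stress biomarkers to the intervention meal will be compared with their response to the control meal", within the same volunteer. Section 4.1 sizes the trial on that basis: "In order to note a 40% difference in the postprandial response of triglycerides and/or LDL-cholesterol".

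The primary endpoint in section 2.2 gives two analytes and a sampling time: "LDL- cholesterol and triglycerides determined at 3h after the meal intake, was set as the primary endpoint of the present, pilot study". It does not mention the fasting value, a change or an increment.

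Sections 1, 3.2 and the text that follows 3.2 provide for a fasting sample in each test period, so every volunteer has a baseline specific to each cheese. Section 6.3 gives it two explicit uses:

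- A check between cheeses: "Differences in baseline values between groups for each biomarker tested, will be analyzed using a paired sample two tailed t test".
- A Wilcoxon signed-rank test of change from baseline, described as within-group.

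The between-cheese analysis is a repeated-measures ANOVA. If time or group is significant, a "multiple comparison post hoc Bonferroni test will be performed for the comparison of concentrations".

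**The concern.** A 3 h concentration is the fasting level on that morning plus whatever the meal added. The two visits are a week apart, with eating habits recorded but not standardised in between. A volunteer whose fasting triglycerides happen to be higher on the Ladotyri day will tend to have a higher 3 h value that day whatever the cheese did. An unadjusted comparison at 3 h carries that day-to-day variation in its error term.

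The baseline t test does not deal with this. A non-significant result in about 10 people does not show that fasting values were equal, and no action is attached to a significant one. The within-cheese Wilcoxon tests use change from fasting but do not compare the cheeses.

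At stake are the precision of the primary comparison and how an observed 3 h difference can be read when fasting values happened to differ.

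**Working it through.** **The plan's own figure.** Section 4.1 states a 40% difference, 80% power, a 5% level, and "a necessary sample of 10 subjects was calculated". It gives no SD, so N = 10 cannot be reproduced forwards. Solving backwards with a two-sided paired t test (noncentral t, 9 df), 80% power at n = 10 needs a standardised difference of 0.996. The implied SD of within-person differences is 40 / 0.996 = 40.2%, in whatever units the 40% is meant.

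**What the 40% could mean.** Assume, for illustration only, fasting triglycerides of 80 mg/dL and a rise of 20, 40 or 60 mg/dL.

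| Rise | 3 h level | 40% of the rise | as % of 3 h level | 40% of the 3 h level |
|---|---|---|---|---|
| 20 | 100 | 8 | 8% | 40 |
| 40 | 120 | 16 | 13% | 48 |
| 60 | 140 | 24 | 17% | 56 |

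The two readings differ by a factor of about 2.3 to 5, and section 4.1 does not say which applies.

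**Precision.** For each volunteer let D0 be the Ladotyri-minus-Parmesan difference in fasting values, D3 the same difference at 3 h, and r their correlation. Assume equal variances. Variances relative to the mean of D3 alone are:

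- change from fasting: 2(1 − r);
- D3 adjusted for D0: (1 − r²)(n − 2)/(n − 3) = (1 − r²) × 8/7 at n = 10.

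The power columns suppose that the unadjusted 3 h contrast has exactly 80% power and hold the absolute difference fixed. The adjusted figures are simulated and count the lost degree of freedom.

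| r (assumed) | Variance, adjusted | Variance, change score | Power, adjusted | Power, change score |
|---|---|---|---|---|
| 0.3 | 0.91 × 8/7 = 1.04 | 1.40 | about 77–78% | 66% |
| 0.5 | 0.75 × 8/7 = 0.86 | 1.00 | about 85% | 80% |
| 0.7 | 0.51 × 8/7 = 0.58 | 0.60 | about 95% | 95% |
| 0.8 | 0.36 × 8/7 = 0.41 | 0.40 | about 99% | 99% |

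Break-even on variance is 1 − r² = 7/8, so r = 0.35. Allowing also for the larger t quantile (2.306 on 8 df against 2.262 on 9 df), it is 1 − r² = (7/8)(2.262/2.306)², so r = 0.40. The plain change score is less precise than the unadjusted contrast whenever r is below 0.5.

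**Error rates with no cheese effect.** In simulation at n = 10 the unadjusted 3 h comparison rejects about 5% of the time overall at every r tried. Restricted to trials whose mean fasting difference exceeds one standard error (about 32% of trials), it rejects about 6%, 8–9%, 11% and 14–15% at r = 0.3, 0.5, 0.7 and 0.9. The adjusted comparison stays near 5% in those same trials.

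**The case against.** **The scale is undefined rather than chosen.** Section 2.2 never says absolute, and sections 3.1 and 4.1 speak of response. This stands: a raw 3 h level is the natural reading of the endpoint and of the comparison of concentrations in 6.3, but it is an inference. What can be said is that no adjustment is specified.

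**The ANOVA may already be baseline-relative.** If the fasting sample is a level of time, which 6.3 neither states nor excludes, the time-by-cheese interaction would compare changes from fasting. This stands only in part. The plan never names that interaction; post hoc testing follows a time or group effect, and what is then compared is concentrations. A time effect alone would trigger it, and section 2.1 expects triglycerides to rise after a cheese meal.

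**A reader might infer that the cheese comparison is biased.** The documents do not support that. Section 1 assigns order at random, so fasting differences between the cheese days are chance and already sit in the paired standard error. Overall type I error stays near 5%.

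**A reader might infer that fasting noise is as large as the effect sought.** In common units it generally is not. With fasting at 80 mg/dL and an assumed day-to-day CV of 15–30%, the standard error of the mean fasting difference is 80 × CV × √(2/10) = 5.4 to 10.7 mg/dL. Against that, 40% of the rise is 8, 16 or 24 mg/dL. The two are comparable only at the smallest rise. If the 40% refers to the 3 h level, the noise is small beside it. No such figures are offered here for LDL-cholesterol.

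**The gain is conditional.** It needs r above about 0.35 to 0.40, and the documents give no r. This stands, and the benefit is therefore called probable.

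**Conclusion.** The point holds as one of specification and efficiency. The aim and sizing concern a response; the primary endpoint is a 3 h determination; and the fasting value collected at both visits is given no stated role in adjusting the between-cheese comparison. The consequences are exposure to chance fasting imbalance in a sample of about 10 and a probable loss of precision. Over assumed r from 0.3 to 0.8, adjustment ranges from 4% more variance to 59% less (1.04 to 0.41). Those ratios rest on equal variances at fasting and 3 h and on an r that is not in the documents, so the size is uncertain although the gap in the text is clear. This is a cheap improvement, not a flaw that invalidates the trial, which calls itself a pilot.

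**What to change.** - **Section 6.3.** For each primary lipid, make the primary analysis the within-volunteer Ladotyri-minus-Parmesan difference at 3 h, adjusted for the within-volunteer difference in fasting values. Report change from fasting as a sensitivity analysis only. Drop the baseline t test as a check of comparability.
- **Section 2.2.** State that the 3 h endpoint is analysed with this adjustment.
- **Section 4.1.** State the scale on which the 40% applies (3 h level, change or rise), with the SD on that scale, so that N = 10 can be checked against the analysis actually planned.

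Cost: wording in three sections, with no new samples or visits. The adjustment uses one degree of freedom and loses slightly if r is below about 0.35 to 0.40. The change-score sensitivity analysis will be less precise than the unadjusted 3 h contrast if r is below 0.5 (variance 1.40 times as large at r = 0.3), so it should not decide the result. Stating the scale in 4.1 may show that N needs to be worked out again.

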3.1. Overview

A nutritional intervention – clinical study of self-comparison design (cross over design: acute study) will take place in a sample of healthy volunteers, where the difference in the effectiveness of the nutritional intervention will be evaluated in the same volunteer. This means that the response of lipemia, glycemia and oxidative stress biomarkers to the intervention meal will be compared with their response to the control meal, in the same volunteer each time. The specific research will be carried out in the specially designed area of

the Human Nutrition unit of the University of the Aegean and in collaboration with the hospital of Lemnos, with which a collaboration protocol has been concluded with the University of the Aegean.

3.2. Study design

In a total sample of approximately 10 healthy volunteers, the number of which was determined through a special statistical program for calculating the required sample of the research to draw safe and reliable conclusions, a nutritional intervention – clinical study of cross-over design will be carried out. The study for each participant will be 7 days long, including the washout period.

Each participant during the first test period and in a state of 12-hour fasting, will be asked to come in the morning hours of 9 am. - 12:30 p.m., the specially designed blood collection room of the Human Nutrition Unit, Department of Food Science and Nutrition, University of the Aegean. In this specially designed area, a blood sample (baseline) will be taken by a doctor or competent staff of the Lemnos Hospital. This will be followed by a discussion with the healthy volunteer, signing of a declaration of participation, filling in a questionnaire and a 24-hour recall of food consumption. The questionnaire that each volunteer will fill out on the first day of the start of the study concerns their medical history and general information about their habits (especially dietary). Afterwards, a meal will be served that will include 2 slices of bread (80g- 40g each) and 2 pieces of cheese (100g- 50g each piece), according to the group each volunteer belongs to, accompanied in each case by 1 glass of water. The consumption of each meal will be completed within the time period of 15 minutes by all participants (controlled). Finally, the following blood samplings will be carried out for the volunteers, which will be conducted 30 minutes, 1.5 and 3 hours after the completion of the meal.

After a seven-day washout period, on the eighth day (2nd test period) the same participants will be asked to come again, in a fasting state, to the specially designed area of the University of the Aegean, at the predetermined morning hours to repeat the procedure nutritional intervention and blood sampling. In other words, a blood sample will be taken by a doctor or competent staff of the Limnos Hospital, followed by a discussion with the volunteer and completion of a 24-hour recall of food consumption questionnaire. The questionnaire that the participants will complete at the start of the second test period is to record their specific eating habits during the washout period (ie the interval between the two periods of the intervention). The meals served to the volunteers are determined by the control or intervention group to which they belong. After each meal is consumed within the 15-min timeperiod, subsequent blood sampling will be done for participants 30, 90, and 180 minutes (min)after the completion of the meal .

4. Enrollment of participants and case of study withdrawal

The goal is to gather an initial sample of people from the Greek area in order to achieve the collection of a required number of cases for study. The research team will then review the inclusion/exclusion criteria and select the participants who will receive the meals in the two test periods of the study.

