6.1. Questionnaires

A specially designed questionnaire, based on bibliographic data, will be used to collect important data regarding the participants of the study.

The questionnaire will concern the clinical condition and habits (especially nutritional) of the volunteers of the clinical study and will include the following parts:

1st part

General socio-demographic and anthropometric data of the study population (gender, age, anthropometric indicators)

2nd part

Clinical status of each participant (medication, dietary supplements, etc.).

3rd part

Dietary and other habits before the start of the intervention, as well as more specific dietary habits for the washout period.

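### Apart from fasting, diet before each visit is recorded but not standardised, which adds avoidable within-person variation to a crossover of about 10 people

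*Combined protocol and SAP*

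**What the plan says.** Section 3.1 sets the comparison within person: each volunteer's response to the intervention meal is set against the same volunteer's response to the control meal. Section 1 divides volunteers at random into two groups, which swap cheeses at the second period after seven days.

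Control before the visits is as follows (section 3.2).

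- Visit 1: the volunteer, "in a state of 12-hour fasting, will be asked to come in the morning hours", gives a baseline sample. After the draw come a discussion, the participation form, and "filling in a questionnaire and a 24-hour recall of food consumption". The test meal follows.
- Visit 2: "the same participants will be asked to come again, in a fasting state". The number of hours is not restated. Blood is taken, "followed by a discussion with the volunteer and completion of a 24-hour recall of food consumption questionnaire".
- Washout: the purpose of the visit 2 questionnaire is "to record their specific eating habits during the washout period". Section 6.1 describes the same item as data collection, covering habits before the intervention "as well as more specific dietary habits for the washout period".

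Section 5.2 assesses compliance only for the supervised meals on site. The supplement and alcohol items in section 4.3 are entry criteria, not rules for the days before a visit. Section 6.3 analyses the biomarkers and gives the recalls and the washout questionnaire no role.

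**The concern.** A crossover gains its efficiency by removing differences between people. What remains is variation within a person from one visit to the other, and prior diet is one source of it that the investigators could reduce. As written, a volunteer can eat Ladotyri or Parmesan during the interval, or have quite different evening meals before the two visits, and still comply fully provided the fast is kept. The plan calls the interval a washout but does not say what is to be avoided in it.

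The records cannot make this good. No rule links a recall to a decision about the visit, and no analysis uses it. Adjusting afterwards for free-form diet data is not realistic with about 10 people. What is at stake is precision in a small study whose sample size has no stated margin.

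**Working it through.** **1. Where prior diet enters the contrast.** Write a volunteer's response at a visit as a personal level, plus a cheese effect, plus an effect g of prior diet, plus error. The within-person difference (Ladotyri minus Parmesan) then contains the cheese effect and the difference in g between the two visits.

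- Variance: whatever varies in g between visits adds to the variance of the within-person difference.
- Bias: let the mean of g be c before visit 1, a before visit 2 for those who had Ladotyri first, and b before visit 2 for those who had Parmesan first. The diet contribution to the contrast is c − a in the first group and b − c in the second. With equal group sizes (an assumption), the average is [(c − a) + (b − c)]/2 = (b − a)/2. This is zero unless diet before visit 2 depends on which cheese came first. A general change in eating between the two visits cancels. Chance imbalance remains possible with 10 people, but that is the noise already counted under variance.

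**2. The plan's own figure.** Section 4.1 gives a 40% difference, 80% power, 5% significance and 10 subjects, with no standard deviation. The figure therefore cannot be reproduced, only back-solved. For a two-sided paired t test (noncentral t, 9 degrees of freedom), n = 10 and 80% power require a standardised difference of 0.996. The implied standard deviation of paired differences is 40/0.996 = 40.2 percentage points. A one-sided test would imply 46.9, and the normal approximation 45.1.

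**3. Sensitivity to added variation (illustration).** Assume that 10 was sized at 40.2 points and that prior-diet variation comes on top. The increases below are assumed; none is in the documents. The last column is 1 − 1/k², where k is the factor by which the standard deviation grows.

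| Increase in SD | SD (points) | Power with 10 | N for 80% | Implied share of total variance |
|---|---|---|---|---|
| none | 40.2 | 80% | 10 | 0% |
| 10% | 44.2 | 72% | 12 | 17% |
| 25% | 50.2 | 61% | 15 | 36% |
| 50% | 60.2 | 47% | 20 | 56% |

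If the unstated standard deviation came from studies that also left diet free, this variation is already inside the 40.2 points. Standardising diet would then raise power above 80% rather than restore it.

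**4. Upper bound on the gain.** Suppose prior diet makes up a share f of the variance of the contrast and matching removed all of it. The standard error would be multiplied by √(1 − f). For an assumed f of 0.2 to 0.4 the factor is 0.894 to 0.775, a reduction of 11% to 23%. Ten matched volunteers would then give the precision of 10/(1 − f) = 12.5 to 16.7 unmatched ones. These are ceilings for that assumed range: repeating one self-reported day cannot remove all diet variation.

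**The case against.** The plan has real safeguards: fasting at both visits, set morning hours, supervised meals of fixed weight, random meal order, a fasting sample at each visit and a paired test of baseline values. The study is also described as a pilot (section 2.2). All of this stands, and it limits the point to precision. The safeguards do not close the gap, however. The fast limits the influence of the previous evening's meal without removing it. The baseline test can show that fasting values differ, but not that prior diet changed the postprandial response, and no action follows from it.

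Three stronger readings are tempting and are not supported.

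- A reader might infer that the two visits are not comparable, or that uncontrolled diet could systematically mimic a cheese effect. With random order, bias needs diet to depend on which cheese came first, and nothing in the documents points to that.
- A reader might infer from section 2.1 that the plan leaves its own hypothesised exposure uncontrolled, since it says of polyphenol-rich foods that "they seem to have a beneficial effect on metabolic biomarkers and pathways, postprandial". That sentence concerns foods eaten in combination with a rich meal. It does not say that food eaten before a fast alters a later response.
- A reader might say that someone who eats a test cheese between visits has not been washed out. Cheese eaten off study is background diet, not carry-over of the period 1 meal, and the documents do not show that it changes the 3-hour lipids.

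Taking the recall after the draw is also a minor matter in itself. It covers the same previous day and still precedes the meal at visit 1. What is missing is a decision rule.

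**Conclusion.** The point holds as a precision improvement. Apart from fasting, diet before each visit is not standardised, neither test cheese is excluded between visits, the visit 2 fasting hours are not restated, and the diet records have no planned use. The likely consequence is avoidable within-person variation and some loss of power.

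The size of the loss cannot be established: the documents give no standard deviation, no within-person correlation and no information on how much prior diet contributes. The power figures and the ceilings above show how sensitive a study of 10 is to added variation; they are not estimates for this trial. The conclusion that bias is not the main issue rests on meal order being random, as section 1 states, and on diet before visit 2 not depending on which cheese was eaten first.

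**What to change.** Amend section 3.2 as follows.

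- At the pre-study briefing (section 4.4), ask volunteers not to eat Ladotyri or Parmesan on the day before visit 1 or at any time until visit 2 is complete. Starting before visit 1 matters: otherwise the visit 1 recall could contain a test cheese, and repeating that day would conflict with avoiding it.
- Give each volunteer a copy of the visit 1 24-hour recall and ask them to repeat that day's food and drink, including the evening meal, on the day before visit 2.
- State the same fasting duration for both visits.
- Complete the visit 2 recall before the test meal, preferably before the fasting draw. Rebook if a criterion written in advance is met, for example a test cheese eaten the previous day or the fast not kept. Record other departures without rebooking.

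The cost is a one-page instruction and a small change in the order of visit 2, using a recall that is already collected. The downside is a small burden on volunteers and an occasional rebooked visit, which would move that volunteer's second visit off day 8.
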